### **7.2.1 Sensitivity Analyses for PFS – Part 1 only**

The following sensitivity analyses will be performed to investigate the impact of potential sources of bias in the primary assessment of PFS.

#### **7.2.1.1 Assessment of Major Deviations**

To assess the impact of major protocol deviations on the primary analysis of PFS, a sensitivity analysis will be performed using the PP analysis set. PFS based on the PP set will be analyzed using a stratified log-rank test, using the methods described for the primary analysis of PFS in Section 7.2. Note, sub-group analyses will not be performed for the sensitivity analysis.

#### **7.2.1.2 Assessment of Informative Censoring**

For Part 1, the primary analysis of PFS is based on an ICR of radiological data. Informative censoring can occur if site believe that a subject has progressed and perform no further radiological assessments in that subject, but the ICR disagree, thus the subject becomes censored at the last available radiological assessment for the ICR assessment of PFS.

To investigate the sensitivity of the primary analysis to this source of bias, a sensitivity analysis will be performed using PFS based on the site assessment of the radiological data. PFS based on site assessments will be analyzed using a stratified log-rank test, using the methods described for the primary analysis of PFS in Section 7.2. Note, the sub-group analyses will not be performed for the sensitivity analysis.

#### **7.2.1.3 Evaluation-Time Bias Assessment**

Bias can be introduced if one treatment arm is assessed more frequently than the other.

For both Parts 1 and Part 2, sensitivity analyses will be performed to assess possible evaluation-time bias that may be introduced if scans are not performed at the protocol-scheduled timepoints. The midpoint between the time of progression and the previous evaluable RECIST assessment will be analyzed using a stratified log-rank test, as described in Section 7.2. This approach has been shown to be robust to even highly asymmetric assessment schedules (Sun and Chen 2010). Note that the sub-group analyses will not be performed for the sensitivity analysis.

#### **7.2.1.4 Attrition-Bias Assessment**

Attrition bias will be assessed by repeating the primary PFS analysis except that the actual PFS event times, rather than the censored times, of subjects who progressed or died in the absence of progression immediately following two, or more, non-evaluable tumor assessments will be included. In addition, subjects who take subsequent therapy prior to progression or death will be censored at their last evaluable assessment prior to taking the subsequent therapy. This analysis will be performed using the methods described in Section 7.2, supported by a Kaplan-Meier plot of the time to censoring where the censoring indicator of the primary PFS analysis is reversed. Note that the sub-group analyses will not be performed for the sensitivity analysis.

### **7.3 Overall Survival**

For Parts 1 and 2, the analysis of OS will test for the superiority of varlitinib-containing treatment arm relative to the placebo-containing arm.

For Part 1, OS will be analyzed at the time of the primary analysis of ORR and PFS. For Part 2, the primary analysis of OS will be performed after the 247th documented OS event.

OS will be analyzed using the methods described in Section 7.2 for the primary analysis of PFS. For Part 2 only, sub-group analyses, as described in Section 7.2, will also be performed.

Subjects whose data contributed to the Part 1 analysis will not contribute to the Part 2 analysis.

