	
To test for heterogeneity across strata, the exact test of Zelen will be performed testing whether the treatment effect differs between the 2 strata included in the primary analysis.
 
Progression-free survival will be analyzed using a stratified log-rank test using the Breslow method to handle ties (Breslow, 1974). The analysis will be stratified by primary tumor location (GB/Non-GB).
 
Overall survival will be analyzed using the methods outlined above for PFS. For Part 1, OS will be analyzed twice. A preliminary analysis of OS will be performed at the time of the primary analysis of ORR and PFS. It is anticipated that the OS data at this time will be immature, thus a second analysis of OS is planned for when approximately 95 patients (approx. 79%) have an OS event. The second analysis of OS will be considered the primary analysis of OS for Part 1 of the trial. For Part 2, the primary analysis of OS will be performed when 247 patients have experienced an OS event. Further details will be provided in the study SAP.
 
Duration of response will be listed and summarized descriptively for the duration of response in responding patients, including the associated Kaplan-Meier curves.
 
Disease control rate will be analyzed using the methods described above for ORR.
 
Tumor size is a secondary endpoint in Part 1 and will be used to assess the exploratory objective of evaluating the role of HER family expression levels as predictors of benefit to varlitinib. Tumor size will be analyzed by analysis of covariance (ANCOVA).
 
Plasma sampling will be conducted for population PK evaluation in Parts 1 and 2 of the study and will use an NLME. PK sampling of all patients is planned for Part 1 of the study while sparse PK sampling is planned for Part 2. For the sparse PK sampling in Part 2, the double-blind design will be maintained and blood samples will be collected from a selected number of patients without limiting the sampling to varlitinib patients only.
 
All PK data will be analyzed according to treatment received. Deviations that have the potential to significantly affect the PK will be reviewed. The population, and decisions regarding which profiles are usable, will be defined by the Study Team Physician, Pharmacokineticist, and Statistician prior to unblinding or any analyses being performed.
 
ECG/QT Analysis (Safety Lead-in and Part 1)
 
General Principles
 
Baseline will be defined as the mean of the triplicate ECG readings performed pre-dose on Day 1. On Day 1, pre-dose is defined as 2 sets of triplicate ECGs taken 45 minutes and 5 minutes prior to dosing. The ECG values from these 2 sets of ECGs will be averaged to create the baseline value. Similarly, for all other time points, for each ECG parameter, each patient's mean will be calculated from the triplicate readings and the mean value will be used.
 
The final ECG assessments (including interval measurements) will be made by the Core ECG laboratory. The Part 1 electrocardiographic Core ECG Laboratory assessments constitute the study's primary assessment of ECG/QTc. Any analysis of ECG data from the Safety lead-in is considered exploratory.
 
Due to the non-randomized, open label design of the Safety lead-in, data from the Safety lead-in will be presented separately from data from Part 1 of the study. Furthermore, ECG/QT outputs will be made available to the DSMB for consideration when determining whether the study should progress to Part 1.

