8 STATISTICAL ANALYSIS

8.1 General Statistical Considerations

All statistical analyses will be performed by the designated CRO, using SAS®, version 9.3 or higher.

Unless specified otherwise, data from the Safety lead-in, Part 1, and Part 2 of the study will be presented separately in the tables, figures, and listings. Patients whose data contributed to the Part 1 analysis will not be included in the Part 2 analysis.

For Parts 1 and 2, for the purpose reporting all FAS and EFR--based endpoints (efficacy data and demography), *Study Day 1* is defined as the date of randomization to study treatment. For visits (or events) that occur on or after randomization, study day is defined as (date of visit [event] -date of randomization + 1). For visits (or events) that occur prior to randomization, study day is defined as (date of visit [event] -date of randomization). There is no Study Day 0.

For Parts 1 and 2, for the purpose of reporting all safety set based endpoints (e.g. AEs, laboratory findings, vital signs, ECG, exposure and dose intensity) and PK set-based endpoints, *Dose Day 1* is defined as the date of first dose of study treatment (referred to in the protocol as Cycle 1 Day 1). For visits (or events) that occur on or after first dose, dose day is defined as (date of visit [event] -date of first dose of study treatment + 1). For visits (or events) that occur prior to first dose, dose day is defined as (date of visit [event] -date of first dose of study treatment). There is no Dose Day 0. For listings (such as for AEs) that include the derivation of “days since last dose,” this is defined as (event date -date of last dose). Events that occur on the same day as the last dose of study drug will therefore be described as occurring zero days from the last dose of study drug.

The database for the Safety lead-in will be locked at the time of the Part 1 analyses. However, interim data from the Safety lead-in will be made available to the DSMB prior to the final DCO to enable the DSMB to review the emerging safety and tolerability data and to advise whether the study can proceed to Part 1. Details of the data to be provided to the DSMB will be provided in the DSMB charter.

The primary analysis of Part 1 will be the later of 3 months after last Patient in or when 70% of the patients (84 patients) have experienced a PFS event. The primary analysis of all primary and secondary endpoints, with the exception of OS, will be performed at this time.

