## 6. General Statistical Considerations

All statistical analyses will be performed by or under the direct auspices of ASLAN Pharmaceuticals, using SAS®, Version 9.2 or higher.

Unless specified otherwise, data from the Safety lead-in, Part 1 and Part 2 will be presented separately in the Tables, Figures and Listings. Subjects whose data contributed to the Part 1 analysis will not be included in the Part 2 analysis.

The database for the Safety lead-in will be locked at the time of the Part 1 analyses. However, interim data from the Safety lead-in will be made available to the DSMB prior to the final data cut-off (DCO), in order to enable the DSMB to review the emerging safety and tolerability data and to advise whether the study can proceed into Part 1. Details of the data to be provided to the DSMB will be provided in the DSMB charter.

The primary analysis of Part 1 will be the later of 3 months after Last Subject In (LSI) or when 70% of the subjects (84 subjects) have experienced a PFS event. At this point, there will be a formal database lock, and the primary analysis of all primary and secondary endpoints will be performed.

The data cut-off for Part 2 will be when 247 OS events have occurred. All secondary endpoints, including ORR, PFS and DoR, will be reported at the time of the primary analysis of OS.

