#### 6.4.2 Interim Analysis

Data from the open-label Safety lead-in will be reviewed on an ongoing basis, and a Data Safety Monitoring Board (DSMB) meeting will occur once the first 12 subjects have completed one cycle of treatment (with a minimum 85% compliance over the first 14 days). The purpose of the initial DSMB meeting is to review the safety and tolerability data prior to commencement of Part 1 of the study.

There are no interim analyses planned during Part 1 or 2. The primary analysis of Part 1 will be the later of 3 months after Last Subject In (LSI) or when 70% of the subjects (84 subjects) have experienced a PFS event. At this time, a database lock will be performed and the primary analysis of all primary and secondary endpoints will be performed. The data cut-off for Part 2 will be following the 247th OS event. Whilst Part 2 is ongoing, further efficacy and safety data may continue to be accrued for Part 1 subjects. For example, further OS events occurring after the primary analysis of Part 1 will continue to be collected and databased.

The database for both parts of the study will be locked at the data cut-off for the Part 2 analyses.

Data for any subjects who continue to receive treatment beyond this point will be reported as a further addendum to the CSR.

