## 6.5 Multiple Testing Strategy

### 6.5.1 Part 1

Part 1 is designed with co-primary endpoints, ORR and PFS. In order to maintain an overall, one-sided 10% type I error rate for Part 1, a **Hochberg** procedure will be used, such that the trial will be deemed to have met its primary objective if either endpoint is significant at the one-sided 5% level, or if both endpoints are significant at the one-sided 10% significance level. If the trial meets its primary objective as described above, all secondary efficacy endpoints will also be tested at the one-sided 10% significance level to better understand the clinical benefit offered by varlitinib treatment.

Furthermore, if the primary objective of the study is met, as described above, statistical significance at the two-sided 5% level will be tested to support marketing approval. For this assessment, the following approach to type I error control will be applied:

- The overall type I error rate for marketing approval will be controlled at the two-sided 5% level, using a Hochberg procedure
- Using this approach, statistical significance may be claimed if *either* ORR or PFS is significant at the two-sided 2.5% significance level or if *both* ORR and PFS are significant at the two-sided 5% significance level.

If statistical significance is demonstrated using the approach described above, the secondary endpoints OS and DCR will also be assessed at the two-sided 5% significance level, in order to further describe the nature of the benefits offered by varlitinib treatment, to support marketing authorisation.

For the purpose of supporting marketing approval, all hypothesis testing at significance levels higher than 5% will be considered exploratory.

### 6.5.2 Part 2

In order to describe the nature of the benefits of varlitinib treatment, OS, ORR, PFS and DCR will all be tested at a 2-sided significance level of 5%.

However, in order to strongly control the type I error at the two-sided 5% level, the following hierarchical testing order is defined for the Part 2 efficacy endpoints: OS – ORR – PFS – DCR.

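### Part 1 overall survival: the protocol's primary analysis is at about 95 deaths, but the SAP plans no such analysis and puts its marketing-support OS test at the earlier ORR/PFS cut-off

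*SAP*

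**What the plan says.** **Protocol.** Section 8.1 takes OS out of the primary analysis at the ORR/PFS cut-off: "The primary analysis of all primary and secondary endpoints, with the exception of OS, will be performed at this time". Sections 8.2.2 and 8.5.2.1 call OS at that cut-off exploratory. They allow a p-value to be shown but rule out any significance claim for marketing authorisation. A second analysis is planned at about 95 deaths (synopsis, 8.1, 8.2.2 and 8.5.2.1). On its status the synopsis says: "The second analysis of OS will be considered the primary analysis of OS for Part 1 of the trial". Section 8.2.2 sets its level at two-sided 5%.

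**SAP.** Section 7.3 gives one time for Part 1 OS: "For Part 1, OS will be analyzed at the time of the primary analysis of ORR and PFS". Section 6 says that at the ORR/PFS cut-off "there will be a formal database lock, and the primary analysis of all primary and secondary endpoints will be performed". Section 6.4.2 repeats this, and neither section excepts OS. Under 6.5.1, once ORR/PFS has succeeded under the two-sided 5% Hochberg rule, "the secondary endpoints OS and DCR will also be assessed at the two-sided 5% significance level", in support of marketing authorisation. For later Part 1 deaths, 6.4.2 says that "further OS events occurring after the primary analysis of Part 1 will continue to be collected and databased", and the next lock it names is this one: "The database for both parts of the study will be locked at the data cut-off for the Part 2 analyses". SAP section 8, which lists changes to the planned analysis, does not mention OS.

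**The concern.** The two documents give the same OS look opposite status. In the protocol it is an early description of data expected to be immature. In the SAP it is the primary analysis of a secondary endpoint and the only place where the marketing-support OS test can fall.

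An analyst who followed the SAP exactly would base an OS claim on the look that the protocol bars from such claims. That analyst would also have no trigger, cut-off or lock for the analysis the protocol calls primary. Protocol 5.4.9 unblinds Part 1 at its cut-off, so a choice between the two looks left until then could be influenced by the result.

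**Working it through.** **Textual comparison**

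| Item | Protocol | SAP |
|---|---|---|
| OS in the primary analysis at the ORR/PFS cut-off | Excepted (8.1) | Included with all secondary endpoints (6, 6.4.2) |
| Status of OS at that cut-off | Exploratory, no marketing claim (8.2.2, 8.5.2.1) | No exploratory label |
| Analysis at about 95 deaths | Planned and primary (synopsis, 8.1, 8.2.2, 8.5.2.1) | Absent |
| Two-sided 5% OS test | At about 95 deaths (8.2.2) | Cut-off not named (6.5.1); only one Part 1 OS analysis exists (7.3) |
| Next lock for Part 1 deaths | Implied at about 95 deaths | Part 2 cut-off (6.4.2) |

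The SAP 7.3 sentence alone would fit the protocol's preliminary look. The conflict appears when it is read with SAP 6, 6.4.2 and 6.5.1.

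**The plan's own figures reproduce**

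- 95/120 = 79.2% (stated: about 79%).
- PFS power, 84 events, HR 0.54, two-sided 5%: Φ(√(84/4) × |ln 0.54| − 1.96) = Φ(0.864) = 80.6% (stated: 80%).
- PFS timing with 60 per arm, exponential PFS, control median 2.67 months, HR 0.54 and cumulative accrual (t/8)²: the 84th event falls at month 12.03 (stated: about 12).

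**How far apart the two OS analyses fall (projection)**

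The documents give no Part 1 OS assumptions. The Part 2 medians are therefore borrowed: 6 and 8.6 months, HR 0.7 (protocol 8.2.3). Accrual over 8 months is taken as (t/8)^k. The Part 2 shape in the synopsis is k = 2; k = 1 and k = 3 are also tried. The cut-off is the later of month 11 (8 + 3) and the 84th PFS event, which gives 11.0, 12.03 and 12.59 months for k = 1, 2, 3.

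Expected deaths per arm = 60 × the average over entry times u of [1 − exp(−ln 2 × (T − u)/median)].

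| Control OS median (months), HR 0.7 | Deaths at cut-off, k = 1 / 2 / 3 |
|---|---|
| 5 | 64.9 / 63.7 / 63.4 |
| 6 | 57.6 / 56.4 / 56.1 |
| 8 | 47.0 / 45.8 / 45.4 |
| 11.2 (figure quoted in protocol 3.3) | 36.2 / 35.1 / 34.7 |

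If OS HR is 1 instead, control medians of 5 to 8 months give about 52 to 72 deaths.

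Two-sided 5% power for HR 0.7 = Φ(√(d/4) × |ln 0.7| − 1.96). Observed HR needed = exp(−2 × 1.96/√d).

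| Deaths d | Power | HR needed |
|---|---|---|
| 35 | 18% | 0.52 |
| 45 | 22% | 0.56 |
| 56 | 27% | 0.59 |
| 65 | 30% | 0.61 |
| 95 | 41% | 0.67 |

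**Timing.** With medians 6 and 8.6 months and k = 2, the 95th death falls at about month 22. The range is 18 to 28 at HR 0.7 with control medians 5 to 8, about 16 to 24 at HR 1, and about 36 with the 11.2-month median at HR 0.7. The SAP's next lock is the Part 2 cut-off. Part 2 starts only after review of Part 1, so on the documents' figures this is month 12 + 31 = 43 at the earliest. By then about 116 of 120 patients would have died (111 to 118; about 102 with the 11.2-month median).

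**Error rate.** Under either document alone there is one two-sided 5% OS test. If both looks were tested at an unadjusted 5%, at 56 and then 95 deaths (correlation √(56/95)), the type I error would be about 8.0%.

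**The case against.** The strongest case against has four parts.

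- **The test's timing is inferred.** SAP 6.5.1 names no cut-off for the marketing-support OS test. That is correct, and it should be read as an inference. It is a firm one, because SAP 6, 6.4.2 and 7.3 leave no other Part 1 OS analysis.
- **The SAP may simply lag the protocol.** The protocol's efficacy analyses are stratified by tumour location alone, while the SAP still plans region and location with a rule for dropping region. That suggests an SAP awaiting update rather than a rival plan. It may explain the conflict, but the SAP would still need correcting.
- **The harm is limited.** Part 1 OS is secondary, no power is stated for it, and the marketing test runs only after ORR/PFS success. A single test at about 56 deaths is valid and needs a more extreme HR; power is low under either plan. All of this stands and limits the severity.
- **The one-sided 10% OS test at the first look is no breach.** This also stands, because for marketing purposes SAP 6.5.1 says "all hypothesis testing at significance levels higher than 5% will be considered exploratory".

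None of these points removes the contradiction over which OS analysis is primary.

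**Conclusion.** The concern holds and should be fixed. The contradiction is textual and needs no arithmetic: the SAP omits the analysis the protocol makes primary and leaves its two-sided 5% OS test at the look the protocol excludes from marketing claims.

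The projection shows that the choice of look matters: about 56 deaths against 95, power about 27% against 41% for HR 0.7, and an observed HR of about 0.59 against 0.67 needed for significance. These figures rest on borrowed Part 2 OS medians, exponential survival, an assumed accrual shape and PFS HR 0.54. If PFS HR were 1, the cut-off would be month 11, with about 50 deaths and 24% power (control OS median 6 months, OS HR 0.7, k = 2).

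The effect is confined to Part 1 OS. Part 1 success on ORR/PFS is untouched, as is the Part 2 OS test, which uses 247 deaths in separate patients. Error is inflated only if both looks are tested at 5%.

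**What to change.** Before unblinding at the Part 1 cut-off, amend the SAP to match the protocol:

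- **6 and 6.4.2:** except OS from the primary analysis at the ORR/PFS lock, and add a data cut-off and lock at about 95 Part 1 deaths.
- **7.3:** describe both OS analyses. Label the first exploratory, with no significance claim for marketing authorisation, and the second primary.
- **6.5.1:** tie the single two-sided 5% OS test to the analysis at about 95 deaths, keeping the existing Hochberg gate. State at which look the one-sided 10% OS test applies, since neither document says so explicitly.
- **10:** rerun the existing OS tables and figures (14.2.3 series) at the second cut-off; their titles name no cut-off, so no new shells are needed.

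The cost is SAP wording, one OS data lock and one rerun. No extra patients, data or follow-up are required: the protocol already plans this analysis and the SAP already keeps collecting Part 1 deaths.

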#### 7.4 Duration of Response

The DoR will not be formally analyzed. DoR will be listed and presented using Kaplan-Meier curves. Descriptive statistics, based on the KM estimates, will be presented by treatment group. For Part 1, DoR will be based on data from the ICR. For Part 2, DoR will be based on site assessments.

#### 7.5 Disease Control Rate

Disease Control Rate will be analyzed using a stratified exact binomial test (Mehta et al, Emerson) which extends Fisher's Exact test to more than one strata. The analysis will be stratified by region (US/Non-US) and primary tumor location (Gall Bladder/Non-GB). The 2-sided p-value will be obtained by doubling the 1-sided p-values.

The conditional maximum likelihood estimate of the odds ratio will be presented together with its exact 2-sided 95% confidence limit, which excludes one if and only if the stratified exact binomial test is significant a 2-sided 5% level. For Part 1 only, corresponding significance levels and confidence intervals will be calculated using tests performed at a 1-sided 10% level. The one-sided p-value will also be presented.

To test for heterogeneity across strata, the exact test of Zelen will be performed testing whether the treatment effect differs between the 4 strata included in the primary analysis.

The primary analysis of DCR will be based on the FAS set. For Part 1 and 2, a sensitivity analysis will also be performed using the EFR.

